9.3. Analysis Populations

9.3.1. Intent-to-Treat (ITT) Population

The ITT population will include all randomized subjects who received IP. This population will be the primary population for efficacy analyses and will be used to summarize all efficacy variables and will summarize subjects as randomized.

9.3.2. Per Protocol (PP) Population

The PP population is a subset of the ITT population, which will include all subjects who complete the study without major protocol deviations. This population will be the secondary population for efficacy analyses and will be used to summarize a subset of efficacy variables. The PP population will summarize subjects as treated.

9.3.3. Safety Population

The safety population will include all subjects who received IP. This population will be used to summarize safety variables and will summarize subjects as treated.

9.4. Demographics and Baseline Characteristics

Subject demographic and baseline characteristics will be summarized in tables. Summary tables will be supported with individual subject data listings.

9.5. Efficacy Endpoints and Analyses

9.5.1. Primary Efficacy Endpoint

Mean change from baseline in total SANDE score at Visit 7/Day 84

9.5.2. Secondary Efficacy Endpoints

- Mean and mean change from baseline at each visit for each of the following evaluations:
 - Conjunctival lissamine green staining (combined and each zone)
 - Corneal fluorescein staining (combined and each zone)
 - TBUT
 - Anesthetized Schirmer's test
 - Conjunctival hyperemia
 - Individual symptom VAS scores, separately for each symptom

- SANDE
 - Mean change from baseline in total SANDE score at each visit
 - Mean total SANDE score at each visit
 - Mean and mean change from baseline in each component of SANDE at each visit

9.5.3. Efficacy Analyses

The primary efficacy endpoint (SANDE) will be summarized using continuous summary statistics by treatment group and visit. The primary analysis will utilize a repeated measures mixed model where the dependent variable is the change from baseline score, treatment group is a fixed effect, baseline score is a covariate, and visit is a repeated measure on subject. The repeated measures mixed model is utilized to account for the effect of missing data under the assumption that the data are missing at random. Least squares means will be used to test each concentration of SDP-4 to vehicle. Sensitivity analyses for the primary endpoint will be performed using last observation carried forward (LOCF) as well as observed data only.

In order to minimize the impact of multiplicity in this dose-response study, the following hierarchy for analyses will be conducted (note: TBUT is one of several secondary outcomes planned to be analyzed, but the sample size was derived using assumptions based on expected SANDE and TBUT values):

1. Primary (SANDE) high concentration vs. vehicle
2. Primary (SANDE) middle concentration vs. vehicle
3. Primary (SANDE) low concentration vs. vehicle
4. Secondary (TBUT) high concentration vs. vehicle
5. Secondary (TBUT) middle concentration vs. vehicle
6. Secondary (TBUT) low concentration vs. vehicle

The comparisons will be conducted at $\alpha = 0.05$. Each comparison will be made in order until $P >$ (exceeds) 0.05. If $P \leq 0.05$, the comparison is statistically significant and testing is continued.

The planned analyses for all efficacy outcomes will be described in detail in the SAP, which will be finalized prior to database lock.

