3. INVESTIGATIONAL PLAN

3.1. Overall Study Design and Plan

This is a Phase 2, multicenter, double-masked, randomized, vehicle-controlled, dose-response, parallel-group study designed to evaluate the ocular and systemic safety and efficacy of SDP-4 ophthalmic solution in subjects with moderate to severe DED in both eyes (OU) over a 12-week (84-day) treatment period.

Subjects will be randomized to 1 of 3 concentrations (0.1%, 1.0% and 3.0%) of SDP-4 Ophthalmic Solution or vehicle in a 1:1:1:1 ratio in parallel groups. All investigational product (IP) (SDP-4 concentrations and vehicle) will be provided in single-use dose (SUD) containers seal packed into foil pouches. Subjects, the Investigator, and all site personnel responsible for performing study assessments will remain masked to treatment assignment.

The IP will be administered via topical ocular instillation, one drop per eye, twice daily (BID) for 12 weeks (84 days). Both eyes will be treated. A 2-week screening/run-in period on BID vehicle will precede the 12-week randomized treatment period.

Subjects must have a Symptom Assessment in Dry Eye (SANDE) total score of ≥ 40 at Visit 1/Screening and Visit 2/Day 1 to enter the trial. For subjects with a qualifying SANDE score who meet all other inclusion/exclusion criteria, the eye with the lower tear break-up time (TBUT) at Visit 2/Day 1 will be designated as the study eye. In the event both eyes have the same TBUT scores, the eye with the lower Schirmer's test score will be designated as the study eye. If both eyes have the same TBUT and Schirmer's test scores, the right eye will be designated as the study eye.

The study will consist of 7 clinic visits, 2 visits during the screening period and 5 on-treatment visits: Visit 1 (Day -14 ± 2 /Screening Visit), followed by the 2-week run-in period on BID vehicle, Visit 2 (Day 1/Confirmatory and Randomization Visit), Visit 3 (Day 7 ± 2), Visit 4 (Day 14 ± 2), Visit 5 (Day 28 ± 2), Visit 6 (Day 56 ± 4) and Visit 7 (Day 84 ± 4 /End of Study Assessments).

If a subject complains of persistent dry eye symptoms, the site may provide the subject with unpreserved artificial tears (provided by the Sponsor), to be used only if necessary. The subject must return all used and unused artificial tears at each visit so the site can conduct accountability to assess the use of artificial tears. Artificial tears may not be used within 2 hours prior to any study visit.

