9.2. Determination of Sample Size

A sample size of 70 subjects per treatment group will have 80% power to detect a treatment difference of 11.7 units in SANDE total score and 1.2 seconds in TBUT at Visit 7/Day 84 using a t-test with a 0.05 two-sided significance level. This calculation is based on the assumptions shown in Table 2. Note: TBUT is one of several secondary outcomes planned to be analyzed, but the sample size was derived using assumptions based on expected SANDE and TBUT values. Over-enrollment of 5 subjects per group/20 subjects per study is planned to account for discontinuations.

Table 2 Sample Sizes: Two-Group t-test of Equal Means

Assumptions	SANDE	TBUT
Test significance level, α	0.050	0.050
1 or 2 sided test	2	2
Difference in means, $\mu_1 - \mu_2$	11.684	1.192
Common standard deviation	24.500	2.500
Effect size, $\delta = \mu_1 - \mu_2 /\sigma$	0.477	0.477
Power (%)	80	80
n per group	70	70

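### The primary SANDE model has no treatment-by-visit term and its least squares means name no visit, so as written it tests an average over Days 7 to 84 instead of the Day 84 endpoint

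*Protocol*

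**What the plan says.** - **Endpoint (Protocol 9.5.1):** "Mean change from baseline in total SANDE score at Visit 7/Day 84". Only this visit is primary.
- **Sample size (Protocol 9.2):** 70 per group for 80% power to detect a "treatment difference of 11.7 units in SANDE total score and 1.2 seconds in TBUT at Visit 7/Day 84", by a two-sided t-test at 0.05.
- **Model (Protocol 9.5.3):** "The primary analysis will utilize a repeated measures mixed model where the dependent variable is the change from baseline score", followed by the role of each term: "treatment group is a fixed effect, baseline score is a covariate, and visit is a repeated measure on subject".
- **Contrast (Protocol 9.5.3):** "Least squares means will be used to test each concentration of SDP-4 to vehicle". No visit is given.
- **Hierarchy (Protocol 9.5.3):** step 1 is "Primary (SANDE) high concentration vs. vehicle". None of the six steps names a visit.
- **Secondary endpoint (Protocol 9.5.2):** "Mean change from baseline in total SANDE score at each visit".
- **Post-baseline visits (Protocol 3.1):** "Visit 3 (Day 7 ± 2), Visit 4 (Day 14 ± 2), Visit 5 (Day 28 ± 2), Visit 6 (Day 56 ± 4) and Visit 7" (Day 84). SANDE is collected at all five (Table 1).

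A treatment-by-visit term appears nowhere in the protocol.

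**The concern.** A repeated measures model gives a treatment difference at a particular visit only if that difference is allowed to vary by visit, which is the job of the treatment-by-visit term. With treatment as the only arm-related term, the model holds one difference per concentration, shared by all five visits. Reading the repeated-measure wording as including a visit main effect does not help. A visit main effect moves all arms together and leaves the arm difference constant.

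The listed model and the stated endpoint therefore describe different quantities unless the effect is flat from Day 7 to Day 84. The protocol does not assume a flat effect: Section 3.2 justifies the 12 weeks partly by wanting to see effects over time, and Section 9.5.2 lists SANDE change visit by visit, which this model cannot estimate by arm.

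Steps 1 to 3 of the hierarchy rest on this model. A slowly building effect would be diluted, and the trial could fail at step 1 despite the planned difference at Day 84. A fading effect could be declared a success on an endpoint where none remains. TBUT (steps 4 to 6) has no stated model, but it is reached only if steps 1 to 3 all pass.

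**Working it through.** **Inputs from the protocol.** Difference 11.684, SD 24.5, 70 per group, two-sided 0.05 (9.2, Table 2); five post-baseline visits at Days 7, 14, 28, 56 and 84 (3.1).

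**Inputs assumed, because the protocol gives none.** SD 24.5 at every visit; complete data; within-subject correlation either equal (0.3, 0.5, 0.7) or AR(1) by visit order (0.5, 0.8); four shapes for the effect over time.

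**Step 1: reproduce the protocol's figure.** SE of the Day 84 difference = 24.5 × √(2/70) = 4.14. Power = Φ(11.684/4.14 − 1.96) = Φ(0.86) = 0.805 by normal approximation, and 0.800 by the noncentral t with 138 df. The stated 70 per group and 80% are correct for a Day 84 comparison.

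**Step 2: what the listed model estimates.** Let V be the 5 × 5 correlation matrix over visits and **1** a vector of ones. A single treatment difference common to all visits has

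- weights w = V⁻¹**1** / (**1**′V⁻¹**1**)
- SE = 24.5 × √(2 / (70 × **1**′V⁻¹**1**))
- rejection in favour of SDP-4 = Φ(w′effect/SE − 1.96)

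| Correlation | Weight on Day 84 | SE |
|---|---|---|
| Equal, 0.3 | 0.200 | 2.75 |
| Equal, 0.5 | 0.200 | 3.21 |
| Equal, 0.7 | 0.200 | 3.61 |
| AR(1), 0.5 | 0.286 | 2.71 |
| AR(1), 0.8 | 0.385 | 3.45 |

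Between 61% and 80% of the weight falls on visits other than the endpoint visit.

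**Step 3: effect shapes at Days 7, 14, 28, 56, 84.**

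- Constant: 11.684 throughout.
- Plateau: linear rise to 11.684 at Day 28, then stable: 2.92, 5.84, 11.68, 11.68, 11.68.
- Linear growth: 11.684 × day/84 = 0.97, 1.95, 3.89, 7.79, 11.68.
- Fade: 11.684 × (1 − day/84) = 10.71, 9.74, 7.79, 3.89, 0.

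Example, linear growth with equal correlation 0.5: the estimate is the plain mean, (0.97 + 1.95 + 3.89 + 7.79 + 11.68)/5 = 5.26; power = Φ(5.26/3.21 − 1.96) = 0.374.

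**Step 4: results over the five correlation structures.**

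| Shape | True Day 84 difference | Estimate, listed model | Rejection for SDP-4, listed model | Rejection for SDP-4, Day 84 contrast |
|---|---|---|---|---|
| Constant | 11.684 | 11.7 | 0.90–0.99 | about 0.80 |
| Plateau by Day 28 | 11.684 | 7.9–8.8 | 0.63–0.89 | about 0.80 |
| Linear growth | 11.684 | 5.3–5.9 | 0.31–0.54 | about 0.80 |
| Fade to zero | 0 | 5.8–6.4 | 0.39–0.65 | about 0.025 |

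A simulation with four arms of 70, a common visit trend in all arms and the covariance estimated from the data (2,000 runs per cell) agreed: constant 0.90–0.99, linear growth 0.30–0.55, and the Day 84 contrast 0.80–0.82 when the true Day 84 difference is 11.684.

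**Step 5: sensitivity to visit spacing.** AR(1) by visit order treats the visits as equally spaced, although the gaps are 7, 14, 28 and 28 days. If correlation instead decays with actual time (assumed 0.3 to 0.8 per 28 days), the Day 84 weight is about 0.31–0.43, linear-growth power 0.42–0.67 and fade rejection 0.32–0.55. The figures move somewhat; the conclusion does not.

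**The case against.** The best defence is to read the protocol as a whole. Steps 1 to 3 are labelled as primary SANDE comparisons, the only primary endpoint is at Day 84, and no sentence announces an average over visits as the target. The model sentence also omits the covariance structure and degrees of freedom, so it may be shorthand for a standard MMRM with visit-specific means. Section 9.5.3 leaves the detail to an SAP that is not at hand, and interaction terms are often settled there.

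That may well be what the authors meant. But Section 9.5.3 does not leave the model open: it assigns a role to each term and states the contrast, and what it states does not yield the endpoint in Section 9.5.1. An SAP that follows it inherits the mismatch; one that adds the interaction changes the stated primary analysis. The two readings give different primary p-values. The LOCF and observed-data sensitivity analyses name no visit or contrast either, so they do not settle it.

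Three parts of the objection stand:

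- The size depends on assumed correlations and shapes, and spacing visits by actual time shifts the ranges (step 5 of the working).
- Nothing in the protocol suggests that the effect falls exactly to zero at Day 84. That case only shows that the type I error rate for the Day 84 hypothesis is not protected.
- The visit-by-visit secondary endpoint is supporting evidence only, since Section 9.5.3 already summarises SANDE by group and visit and does not say that the primary model must supply those results.

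**Conclusion.** The concern holds. Followed as written, Section 9.5.3 tests one covariance-weighted difference over Days 7 to 84, while the endpoint and the sample size are for Day 84. That follows from the listed terms and needs no assumption. The two agree only if the effect is the same at every visit; in that case the across-visit test is valid and more powerful.

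The consequences in other cases do rest on assumptions. Under those set out above, power for the planned Day 84 difference can fall to roughly 0.3 to 0.5 with linear growth, and a success can be declared in roughly 40% to 65% of trials with no Day 84 effect if the effect fades. Because this is the primary test and the gate to every later step, it should be corrected before unmasking.

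**What to change.** In Section 9.5.3:

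1. List treatment, visit, treatment-by-visit and baseline as fixed effects, keeping visit as the repeated factor within subject.
2. State that the test at each of steps 1 to 3 is the least squares mean difference from vehicle at Visit 7/Day 84.
3. If the same model is used for TBUT, state the same Day 84 contrast for steps 4 to 6.

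The SAP should carry the same wording. The cost is a change of text and a few degrees of freedom; the sample size is unchanged. If the effect really is constant over time, the Day 84 contrast gives up power against the across-visit test (about 0.80 against 0.90–0.99), but 0.80 is what the trial was sized for.

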4.2. Inclusion Criteria

Individuals must meet the following criteria at Screening (Visit 1/Day -14) and Visit 2/Day 1:

1. Willing and able to understand and sign an informed consent form prior to any study-related procedures.
2. Male or female patients 18 years of age or older.
3. Willing and able to follow study instructions, able to self-administer IP or have IP administered by a caregiver throughout the study period, and able to be present for the required study visits/assessments for the duration of the study.
4. Have DED in both eyes, as supported by a subject-reported history of daily symptoms of dry eye for ≥ 6 months prior to Visit 1/Screening.
5. Total score ≥ 40 on the Symptom Assessment in Dry Eye (SANDE) questionnaire.
6. History of artificial tear use in the 30 days prior to Visit 1/Screening and willingness to discontinue use during the study.
7. Tear break-up time (TBUT) of ≤ 6 seconds in both eyes.
8. Anesthetized Schirmer's test tear volume ≥ 3 mm and <10 mm in both eyes.
9. Best-corrected visual acuity (BCVA) of $+0.7$ logMAR or better in each eye as assessed by logMAR chart.
10. Female patients must be 1 year postmenopausal, surgically sterilized, or females of childbearing potential with a negative urine pregnancy test at Visit 1/Screening. Females of childbearing potential must use an acceptable form of contraception throughout the study. Acceptable methods include the use of at least one of the following: intrauterine device (IUD), hormonal (oral, injection, patch, implant, ring), barrier with spermicide (condom, diaphragm), or abstinence.

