5.2. Selection, Timing and Administration of Dose for Each Patient

Subjects will be randomized to treatment with 1 of 3 concentrations (0.1%, 1.0% and 3.0%) of SDP-4 Ophthalmic Solution or vehicle which will be administered to each eye BID, approximately 12 hours apart, for 84 days.

Subjects (or their caregiver, if the subject is not able to self-administer the IP) will administer IP topically OU BID for 84 days. At the Screening and Baseline visits, site personnel will instruct the subject (or caregiver) in topical ocular drop administration procedures. After instilling a drop in each eye, the used single-use dose (SUD) should be stored in the storage container provided by site personnel and placed back in the box.

Twice each day, approximately 12 hours apart, the subject (or caregiver) will open a new SUD and administer 1 drop to each eye, store the used SUD in the foil pouch, and place it in the box (or storage container) for return to the clinical site so accountability can be documented in the source document and electronic case report form (eCRF). All IP, including the box, used SUDs/foil pouches and any unopened SUDs will be returned to the clinical site where the used and unopened IP will be documented at Visits 2 through 7.

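### The primary SANDE model in 9.5.3 uses one baseline score, although a second pre-randomization SANDE score (Visit 1) is already collected; adding it could gain some power at almost no cost

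*Protocol*

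**What the plan says.** Section 9.5.3 takes change from baseline in SANDE as the dependent variable and states that "treatment group is a fixed effect, baseline score is a covariate, and visit is a repeated measure on subject". It names no other covariate and leaves further detail to the SAP.

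Section 3.1 requires a SANDE "total score of ≥ 40 at Visit 1/Screening and Visit 2/Day 1 to enter the trial". Section 4.2 applies its entry criteria at both visits: "Individuals must meet the following criteria at Screening (Visit 1/Day -14) and Visit 2/Day 1". Table 1 and sections 7.1 and 7.2.1 schedule SANDE at both. Between the two readings, "A 2-week screening/run-in period on BID vehicle will precede the 12-week randomized treatment period".

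The protocol has no formal definition of baseline. Section 5.2 treats screening and baseline as separate visits ("At the Screening and Baseline visits, site personnel will instruct the subject (or caregiver) in topical ocular drop administration procedures"), so Visit 2/Day 1 is the natural reading, but it is an inference.

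Section 9.2 sizes the trial with an unadjusted two-group t-test: 70 per group for "80% power to detect a treatment difference of 11.7 units in SANDE total score and 1.2 seconds in TBUT at Visit 7/Day 84". No gain from any covariate is counted.

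**The concern.** A covariate measured before randomization improves precision to the extent that it predicts the Day 84 outcome. The Visit 2 score is one self-rated measurement, and the entry rule removes everyone below 40, which narrows its range and weakens its correlation with Day 84. The Visit 1 score measures the same quantity two weeks earlier, is required for eligibility, and therefore exists for every eligible randomized subject. Two such readings can predict Day 84 better than one.

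What is at stake is precision, not validity. The three SANDE comparisons come first in the fixed testing sequence of 9.5.3, and testing stops at the first one that fails. A smaller residual variance would help each of those three steps and so the chance of getting past them.

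**Working it through.** **Inputs from the protocol.** Section 9.2 and Table 2: SANDE difference 11.684, common SD 24.5, two-sided alpha 0.05, 70 per group, power 80%. Section 3.1: SANDE at least 40 at both pre-randomization visits. Section 6.3.1.1: score range 0 to 100.

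**Inputs assumed.** The correlations among Visit 1, Visit 2 and Day 84, and the mean and SD of SANDE before selection, are not in the protocol. Table 2 does not say whether 24.5 is the SD of the score, of the change, or of the residual. The main calculation takes it as the residual SD after adjusting for one baseline.

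**Step 1: the plan's own figure.** Effect size = 11.684 / 24.5 = 0.477. Noncentral-t power at 70 per group is 80.0%. The stated figure reproduces.

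**Step 2: equal correlations r, no selection.** In units of the outcome variance, residual variance is
- one reading: 1 − r²
- two readings: 1 − 2r²/(1 + r)
- ratio, two over one: (1 + 2r)/(1 + r)²

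| r | ratio | power at 70 per group |
|---|---|---|
| 0.3 | 1.6/1.69 = 0.947 | 82.1% |
| 0.5 | 2.0/2.25 = 0.889 | 84.4% |
| 0.7 | 2.4/2.89 = 0.830 | 86.7% |

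Power is recomputed with SD 24.5 × √ratio.

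**Step 3: equal correlations with the entry rule.** Trivariate normal simulation, mean 60 to 65, SD 20 to 24.5, keeping subjects with both pre-randomization scores between 40 and 100.

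| r before selection | ratio | power at 70 per group |
|---|---|---|
| 0.3 | 0.97 to 0.98 | about 81% |
| 0.5 | 0.93 to 0.94 | 82 to 83% |
| 0.7 | 0.87 to 0.89 | 84 to 85% |

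The cut in residual variance is thus about 2 to 13%. At the extremes, 70 × 0.977 = 68.4 and 70 × 0.871 = 61.0, so the gain is worth about 2 to 9 subjects per group.

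**Step 4: Visit 1 less correlated with Day 84 than Visit 2.** The ratio is 1 − p², where p is the partial correlation of Visit 1 with Day 84 given Visit 2:

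p = (r17 − r12·r27) / √[(1 − r12²)(1 − r27²)]

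Take r12 = 0.7 (Visit 1 with Visit 2) and r27 = 0.5 (Visit 2 with Day 84). Then r12·r27 = 0.35 and the denominator is √(0.51 × 0.75) = 0.618.

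| r17 (Visit 1 with Day 84) | p | ratio | power |
|---|---|---|---|
| 0.35 | 0 | 1.000 | 80.0% |
| 0.40 | 0.05/0.618 = 0.081 | 0.9935 | 80.3% |
| 0.45 | 0.10/0.618 = 0.162 | 0.974 | 81.0% |

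These three rows ignore the entry rule. It leaves the first row at zero gain and makes the other two gains smaller still.

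**Step 5: other readings of 24.5.** Without selection, at r = 0.3 / 0.5 / 0.7:
- as the SD of change, power with one reading is 93.5 / 89.9 / 86.0% and with two 94.6 / 92.9 / 91.5%
- as the SD of the Day 84 score, power with one reading is 83.6 / 89.9 / 97.5% and with two 85.5 / 92.9 / 99.0%

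The direction is the same on either reading.

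**The case against.** The strongest reply is that nothing in 9.5.3 is wrong. A mixed model adjusted for one baseline is standard, the sample size rests on an unadjusted t-test, and the section defers detail to the SAP. All of that stands, and it is why the point is only an efficiency improvement. It remains worth making because 9.5.3 does fix the covariate of the primary model.

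The second reply concerns size. Equal correlation favours the proposal. Visit 1 is two weeks further from Day 84 and precedes the vehicle run-in, while Visit 2 follows two weeks on the product that the control group goes on using. The entry rule truncates Visit 1 as well as Visit 2. This also stands: the gain can be zero, and a range that starts above zero would mislead.

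Three stronger readings are tempting and are not supported:
- *That the extra power is certain.* It depends on a partial correlation that the protocol does not supply.
- *That the TBUT analysis has the same gap.* Visit 1 TBUT is collected (section 4.2 requires "Tear break-up time (TBUT) of ≤ 6 seconds in both eyes" at both visits), but the model sentence in 9.5.3 describes the SANDE analysis, and no TBUT model is fixed. Section 6.3.2.1 also already averages two TBUT measurements per eye.
- *That the covariates should have visit-specific slopes.* That is a separate modelling choice, which the figures above do not address.

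**Conclusion.** The point holds as an optional gain in efficiency for the primary SANDE model. A second pre-randomization SANDE score exists for every eligible randomized subject and is left unused. Because it is measured before randomization, adjusting for it does not bias the treatment comparison. Leaving Visit 2 as the reference for change keeps the quantity being estimated the same.

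Under assumed equal correlations of 0.3 to 0.7, with the entry rule applied and 24.5 read as the residual SD after one baseline, the gain is about 1 to 5 power points. If Visit 1 carries little beyond Visit 2, it is 0 to 1 point. A reader might infer that the trial is underpowered or the primary analysis flawed; neither follows, since the 80% power at 70 per group reproduces without any covariate gain.

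**What to change.** In section 9.5.3, and correspondingly in the SAP, before unmasking, write: *the Visit 2/Day 1 baseline score and the Visit 1/Screening score (from the screening that led to randomization) are covariates; change from baseline remains relative to Visit 2.* The words in parentheses are needed because section 6.9 allows rescreening under the same subject number, so a subject may have more than one Visit 1 score. The wording also settles which visit is baseline.

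If the SAP uses the same model for TBUT, the study eye's Visit 1 TBUT can be added in the same way.

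The cost is one sentence and about one degree of freedom. No visit, procedure or subject is added, and missing Visit 1 scores should not arise among eligible subjects because the score is needed for entry.
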